8.2.1. Sentinel Events

A Sentinel Event is a GSK-defined SAE that is not necessarily drug-related but has been associated historically with adverse reactions for other drugs and is therefore worthy of heightened pharmacovigilance. The GSK Medical Monitor is accountable for reviewing all SAEs for possible Sentinel Events which is mandated at GSK. The GSK medical monitor may request additional clinical information on an urgent basis if a possible Sentinel Event is identified on SAE review. The current GSK-defined Sentinel Events are listed below:

- Acquired Long QT Syndrome
- Agranulocytosis/Severe Neutropenia

- Anaphylaxis & Anaphylactoid Reactions
- Hepatotoxicity
- Acute Renal Failure
- Seizure
- Stevens Johnson syndrome/Toxic epidermal necrosis

8.3. Laboratory and Other Safety Assessment Abnormalities Reported as AEs and SAEs

Any abnormal laboratory test results (hematology, clinical chemistry, or urinalysis), or other safety assessments (e.g., electrocardiogram [ECGs], radiological scans, vital signs measurements) including those that worsen from baseline, and events felt to be clinically significant in the medical and scientific judgment of the investigator are to be recorded as an adverse event (AE) or serious adverse event (SAE), in accordance with the definitions provided.

In addition, an associated AE or SAE is to be recorded for any laboratory test result or other safety assessment that led to an intervention, including permanent discontinuation of study treatment, dose reduction, and/or dose interruption/delay.

Any new primary cancer must be reported as a SAE.

However, any clinically significant safety assessments that are associated with the underlying disease, unless judged by the investigator to be more severe than expected for the subject's condition, are not to be reported as AEs or SAEs.

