2. OBJECTIVE(S), ENDPOINT(S) AND HYPOTHESIS

Hypothesis

GSK2857916 can be safely administered to subjects with MM and with other BCMA positive malignancies at doses where target engagement can be demonstrated.

Objective	Endpoint
Primary	

 To determine safety, tolerability, maximum tolerated dose (MTD), and recommended phase (RP2) dose and schedule of GSK2857916 administered 	
 Adverse events (AE) and changes in clinical signs and laboratory parameters
Secondary	

 To evaluate the pharmacokinetic (PK) profile of GSK2857916 and the breakdown product cys-mcMMAF) after intravenous (IV) single and repeat dose administration in subjects with relapsed/refractory MM and BCMA expressing lymphomas 	
 GSK2857916 and cys-mcMMAF PK parameters following IV single and repeat dose administration during dose escalation as data permit (e.g., AUCs C_{max}, t_{max}, CL, V_{SS}, t_{1/2} [single dose], C_{max} and C_{trough} [repeat dose]). GSK2857916 population PK parameters in expansion cohorts at the RP2 dose (e.g. clearance (CL), volume of distribution (V_d)), and relevant covariates which may influence exposure (e.g. age, weight, or disease-related covariates e.g. BCMA expression)

Objective	Endpoint

 To assess anti-drug antibody (ADA) formation after IV single and repeat dose administration of GSK2857916 	
 ADA incidence and titers after single and repeat IV dosing of GSK2857916

 To explore the initial anti-tumor activity of GSK2857916 in subjects with relapsed/refractory MM and BCMA expressing lymphomas 	
 Clinical activity measured as Overall Response Rate (ORR) which is defined as follows: 
 For MM: the percentage of subjects achieving confirmed partial response or better (\geqPR) In addition, the percentage of subjects with minimal response (MR) will be assessed for clinical benefit rate (CBR) (Appendix 1) For Lymphomas: the percentage of subjects achieving PR or better (\geqPR) (Appendix 2)
Exploratory	

 To evaluate PD markers in MM after treatment with GSK2857916 	
 sBCMA levels, BCMA receptor occupancy and cell death markers in subjects with MM.

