	Grade 4: \leq 25x10 ⁹ /L	
 • Withhold the dose. Consider restarting with 25% dose reduction if recovered to >25x 10⁹/L , only if there is no active bleeding at time of treatment re-start • If thrombocytopenia is considered disease related, is not accompanied by bleeding, and recovers with transfusion to >30 x10⁹/L within 14 days, restarting treatment at 50% dose reduction may be considered after discussion with the GSK Medical Monitor
Febrile neutropenia	>38.3°C for > 1 hr AND ANC < 1000/mm ³	
 • Withhold GSK2857916, implement treatment with antibiotics, antivirals and antifungals, as clinically indicated, • If resolved \leq 14 days, may restart GSK2857916 treatment at 25% dose reduction

Toxicity	Grade/symptoms	Recommendations
INR prolongation	> 1.5	
 • Evaluate liver function and other possible causes for INR elevation (use of anticoagulants, work up for DIC and provide treatment as clinically indicated 
 – If subject meets liver stopping criteria: Withdraw from study treatment as per liver stopping criteria – If subject has evidence of DIC: withdraw subject from study treatment – If isolated INR elevation and subject does not meet liver stopping criteria 
 • Withhold the dose and re-test INR within 48hrs • Discuss the case with Medical Monitor and consider 25% dose reduction
	> 2.0	
 • Evaluate possible reasons as above, treat adequately if underlying condition has been identified • Restart treatment with GSK2857916 at 25-50% dose reduction if toxicity resolved to ≤ 1.5 baseline and after discussing the case with GSK Medical Monitor
	>2.5	
 • Evaluate and provide medical treatment if necessary • If INR prolongation is not related to use of anticoagulants withdraw subject from study treatment
Ocular/corneal toxicity	Grade 1	
 • Continue treatment with current dose of GSK2857916. • Consult ophthalmologist within 7 days

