13.7.2.2. Adverse Events

Adverse events (AEs) will be coded using the standard MedDRA and grouped by system organ class. Adverse events (AEs) will be graded by the investigator according to the National Cancer Institute- Common Toxicity Criteria for Adverse Events (NCI-CTCAE), (version 4).

Events will be summarized by frequency and proportion of total subjects, by system organ class and preferred term. Separate summaries will be given for all AEs, treatment-related AEs, serious adverse events (SAEs) and AEs leading to discontinuation of study treatment. Adverse events (AEs), if listed in the NCI-CTCAE (version 4) will be summarized by the maximum grade. Otherwise, the AEs will be summarized by maximum intensity.

Characteristics (e.g. number of occurrences, action taken, grade, etc) of the following AEs of clinical interest will be summarized separately: corneal events, hematologic toxicities (including but not limited to thrombocytopenia and neutropenia), infusion related reaction etc. Details will be provided in the RAP.

The incidence of deaths and the primary cause of death will be summarized.

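### Section 8.3 does not say whether a disease-attributed laboratory abnormality that led to a dose change is recorded as an AE, so AE-based cytopenia summaries may be incomplete and uneven between investigators.

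*Protocol*

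**What the plan says.** Section 8.3 of the protocol, second paragraph: "an associated AE or SAE is to be recorded for any laboratory test result or other safety assessment that led to an intervention". Permanent discontinuation, dose reduction and dose interruption or delay are listed as interventions. No exception is made for cause.

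The last paragraph of 8.3 is introduced as a contrast. It excludes "any clinically significant safety assessments that are associated with the underlying disease" from AE and SAE reporting, "unless judged by the investigator to be more severe than expected" for the subject's condition. Section 8.1 has a parallel exclusion in the AE definition for expected signs, symptoms or progression of the disease under study.

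The Grade 4 thrombocytopenia row of section 3.10.2 has the dose withheld and then adds a branch for disease attribution: "If thrombocytopenia is considered disease related, is not accompanied by bleeding, and recovers with transfusion" above a stated count within 14 days, "restarting treatment at 50% dose reduction may be considered after discussion with the GSK Medical Monitor".

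Section 2 defines the primary endpoint as "Adverse events (AE) and changes in clinical signs and laboratory parameters". Section 13.7.2.2 plans separate summaries, with features such as grade and action taken, for AEs of clinical interest, among them "hematologic toxicities (including but not limited to thrombocytopenia and neutropenia". Section 13.7.2.3 summarizes worst-case hematology and chemistry grades and shifts from baseline.

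**The concern.** Myeloma lowers blood counts, and the protocol also expects the drug to do so. For a cytopenia that changes dosing, the question of disease or drug will therefore arise, and this study has one arm and no blinding to help answer it. Under 8.3 that attribution decides whether the event is recorded at all, when it could simply be an attribute of a recorded event. Two investigators with the same patient could act differently, and each could cite 8.3 in support.

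This is a data-collection rule. An AE that was never entered cannot be restored at analysis, so an analysis plan cannot repair it. What is at stake is the completeness of the AE-based description of hematologic toxicity, and in particular of how often a cytopenia changed dosing.

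**Working it through.** The protocol gives no figure for this point, so the check sets the sections side by side and follows the foreseen case through them.

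**1. Do the two rules overlap?** The intervention rule covers every laboratory result that led to a dose change, whatever its cause. The exclusion covers every clinically significant disease-associated finding that is not worse than expected, whatever its consequence. A result that is disease-associated, not worse than expected and followed by a dose change meets both. Section 8.3 does not say which then governs.

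**2. Does the protocol foresee such a result?** Yes, in the 3.10.2 branch for Grade 4 thrombocytopenia. The investigator considers it disease related, the dose is withheld (an interruption), and a reduced-dose restart may follow (a reduction). The intervention rule requires an AE. The exclusion forbids one unless the event is judged worse than expected, a term that the protocol does not define.

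**3. Where does the event appear under each reading?**

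| Output | Intervention rule governs | Exclusion governs |
|---|---|---|
| All-AE summary (13.7.2.2) | Included | Absent |
| Hematologic AEs of clinical interest, with action taken (13.7.2.2) | Included | Absent |
| Worst-case grade and shift tables (13.7.2.3) | Included | Included |
| DLT assessment, Part 1 (3.3.3) | Own test: drug relationship cannot be ruled out | Same test |

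The laboratory tables keep the value and the grade. They are not planned to show the action taken.

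**4. Size.** Let k be the number of subjects in a full Part 2 myeloma cohort whose only AE of a given type is one of these events. The two readings then differ in reported incidence by k/40. For k = 1 this is 1/40 = 0.025, or 2.5 percentage points. The protocol states neither an expected rate of dose-modifying cytopenia nor the share that would be attributed to disease, so k cannot be derived from it.

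**The case against.** The strongest case on the other side is that the overlap is narrow and largely covered elsewhere.

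- **The contrast word may settle it.** The last paragraph can be read as an exception to what precedes it, so this is an unresolved overlap and not an unavoidable contradiction. That stands. But the exception reading is the one that removes dose-changing cytopenias from the AE data, and the opposite reading remains open to a site.
- **The severity qualifier brings some events back.** Entry requires platelets of at least 50 x 10^9/L (Table 14), so an on-study Grade 4 value lies below the qualifying count, and 8.1 counts an increase in grade of a pre-existing condition as an AE. This reduces the loss. It does not remove it, because 8.1 also excludes expected progression of the disease under study.
- **Only one 3.10.2 branch ties a dose reduction to a disease-attributed cytopenia.** That stands. The albuminuria row interrupts dosing only where there is no clear evidence of disease progression, and Table 13 applies to toxicities possibly related to the drug, so neither shows the same collision.
- **Consequences are partly captured elsewhere.** Section 6.3 puts the primary reason for permanent discontinuation in the eCRF, and 4.4 has administration reported there. The foreseen case is also a restart, so it does not demonstrate a loss from the table of AEs leading to discontinuation.
- **Attribution is not wholly private.** The restart needs discussion with the Medical Monitor, and section 12.1 provides for cross-site safety meetings. Different recording between investigators is therefore possible but not shown.

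A reader might go further and infer that these cytopenias drop out of the primary safety endpoint. They do not: that endpoint includes laboratory parameters, and 13.7.2.3 summarizes the grades whether or not an AE was entered. Nor does the point undermine the MTD, since the DLT test in 3.3.3 does not rest on 8.3.

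**Conclusion.** The point holds as an unresolved overlap in 8.3 with a case that the protocol itself foresees. If the exclusion is applied, a disease-attributed cytopenia that changed dosing is missing from the AE component of the primary safety endpoint and from the hematologic AE-of-clinical-interest summary. Its grade remains visible in the laboratory tables. Recording may differ between investigators in this open-label, single-arm study.

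The only size the protocol supports is 2.5 points per subject at 40 subjects. A reader might want to attach a percentage bias, but that needs an assumed event rate and an assumed share attributed to disease, and neither is in the document. It would also overstate the matter to call every omitted event a bias in drug toxicity: where the disease attribution is correct, what is lost is completeness of the AE record. The conclusion assumes that at least some such events would not be judged worse than expected. The correction is worth making because it is cheap and the data cannot be recovered later.

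**What to change.** Add one sentence to the last paragraph of 8.3: the disease-associated exclusion does not apply to a result that led to interruption, reduction or discontinuation of dosing. Such a result is recorded as an AE, with disease or study treatment captured as its causality. Make the parallel exclusion in section 8.1 consistent with this; otherwise the AE definition would contradict the new sentence. The change should go no wider than results that led to a dose change, since that is where the two rules meet. It concerns recording only and leaves every dose and management rule as it is.

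The cost is a short text change in two sections and a note to sites, with somewhat more AE entries and slightly higher reported AE rates.

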8.3.1. Cardiovascular Events

Investigators will be required to fill out event specific data collection tools for the following AEs and SAEs:

- Myocardial infarction/unstable angina
- Congestive heart failure
- Arrhythmias
- Valvulopathy
- Pulmonary hypertension
- Cerebrovascular events/stroke and transient ischemic attack
- Peripheral arterial thromboembolism
- Deep venous thrombosis/pulmonary embolism
- Revascularisation

This information should be recorded in the specific cardiovascular eCRF within one week of when the AE/SAE(s) are first reported.

8.4. Disease-Related Events and/or Disease-Related Outcomes Not Qualifying as SAEs

An event which is part of the natural course of the disease under study (i.e., disease progression or hospitalization due to disease progression) does not need to be reported as a serious adverse event (SAE). Death due to disease under study is to be recorded on the Death electronic case report form (eCRF). However, if the underlying disease (i.e., progression) is greater than that which would normally be expected for the subject, or if the investigator considers that there was a causal relationship between treatment with study treatment(s) or protocol design or procedures and the disease progression, then this must be reported as a SAE.

8.5. Time Period and Frequency of Detecting AEs and SAEs

The investigator or site staff is responsible for detecting, documenting and reporting events that meet the definition of an adverse event (AE) or serious adverse event (SAE).

AEs will be collected from the time the first dose of study treatment is administered until 30 days following discontinuation of study treatment regardless of initiation of a new cancer therapy or transfer to hospice.

SAEs will be collected over the same time period as stated above for AEs. In addition, any SAE assessed **as related** to study participation (e.g., protocol-mandated procedures, invasive tests, or change in existing therapy), study treatment or GSK concomitant medication must be recorded from the time a subject consents to participate in the study up to and including any follow-up contact. All SAEs will be reported to GSK within 24 hours, as indicated in Section [8.5.2](#).

After discontinuation of study treatment, the investigator will monitor all AEs/SAEs that are ongoing until resolution or stabilization of the event or until the subject is lost to follow-up. At any time after 30 days the investigator may report any AE that they believe possibly related to study treatment.

8.5.1. Method of Detecting AEs and SAEs

Care must be taken not to introduce bias when detecting AEs and/or SAEs. Open-ended and non-leading verbal questioning of the subject is the preferred method to inquire about AE occurrence. Appropriate questions include:

“How are you feeling?”

“Have you had any (other) medical problems since your last visit/contact?” or for pediatric studies, “Has your child had any (other) medical problems or seem to act differently in any way since his/her last visit/contact?”

“Have you taken any new medicines, other than those provided in this study, since your last visit/contact?” or for pediatric studies, “Has your child needed to take any medicines, other than those provided in this study, since his/her last visit/contact?”

8.5.2. Prompt Reporting of SAEs and Other Events to GSK

Serious adverse events (SAEs), pregnancies, and liver function abnormalities and any other events meeting pre-defined criteria will be reported promptly by the investigator to GSK as described in the following table once the investigator determines the event meets the protocol definition for that event.

Type of Event	Initial Reports		Follow-up Information on a Previous Report	
	Time Frame	Documents	Time Frame	Documents
All SAEs	24 hours	SAE data collection tool	24 hours	Updated SAE data collection tool
“CV events” and/or “death”	Initial and follow up reports to be completed within one week of when the cardiovascular event or death is reported	“CV events” and/or “death” data collection tool(s) if applicable	Initial and follow up reports to be completed within one week of when the cardiovascular event or death is reported	Updated “CV events” and/or “death” data collection tool(s) if applicable
Pregnancy	2 Weeks	Pregnancy Notification Form	2 Weeks	Pregnancy Follow-up Form
Liver chemistry abnormalities:				
ALT ≥ 3 times ULN and bilirubin ≥ 2 times ULN (>35% direct) (or ALT ≥ 3 times ULN and INR >1.5, if INR is measured) ^c	24 hours ^a	SAE data collection tool; Liver Event eCRF and liver imaging and/or biopsy eCRFs if applicable ^b	24 hours	Updated SAE data collection tool. Updated Liver Event eCRF ^b
ALT ≥ 5 times ULN; ALT ≥ 3 times ULN with hepatitis or rash or 3 times ULN ≥ 4 weeks	24 hours ^a	Liver Event eCRF ^b	24 hours	Updated Liver Event eCRF ^b
ALT ≥ 3 times ULN and <5 times ULN and bilirubin <2 times ULN	24 hours ^a	Liver Event eCRF does not need to be completed unless elevations persist for 4 weeks or subject cannot be monitored weekly for 4 weeks ^b		

- GSK to be notified at onset of liver chemistry elevations to discuss subject safety.
- Liver event documents should be completed as soon as possible
- INR measurement is not required; if measured, the threshold value stated will not apply to subjects receiving anticoagulants.

Methods for detecting, recording, evaluating, and following up on adverse events (AEs) and serious adverse events (SAEs) are provided in the Study Procedures Manual (SPM).

8.5.3. Regulatory reporting requirements for SAEs

Prompt notification of serious adverse events (SAEs) by the investigator to GSK is essential so that legal obligations and ethical responsibilities towards the safety of subjects are met.

GSK has a legal responsibility to notify both the local regulatory authority and other regulatory agencies about the safety of a product under clinical investigation. GSK will comply with country specific regulatory requirements relating to safety reporting to the regulatory authority, institutional review board (IRB)/ethics committee (EC) and investigators.

Investigator safety reports are prepared for suspected unexpected serious adverse reactions according to local regulatory requirements and GSK policy and are forwarded to investigators as necessary.

An investigator who receives an investigator safety report describing a SAE(s) or other specific safety information (e.g., summary or listing of SAEs) from GSK will file it with the IB and will notify the IRB/EC, if appropriate according to local requirements.

9. LIVER CHEMISTRY FOLLOW-UP PROCEDURES

9.1. Liver Chemistry Testing Procedures

For subjects meeting any of the liver chemistry stopping criteria in Section 3.9.1, make every attempt to carry out the **liver event follow-up assessments** described below:

- Viral hepatitis serology, including:
 - Hepatitis A IgM antibody
 - Hepatitis B surface antigen and Hepatitis B Core Antibody (IgM)
 - Hepatitis C RNA
 - Cytomegalovirus IgM antibody
 - Epstein-Barr viral capsid antigen IgM antibody (or if unavailable, then obtain heterophile antibody or monospot testing)
- Blood sample for pharmacokinetic (PK) analysis. Record the date and time of the PK blood sample draw and the date and time of the last dose of study drug prior the blood sample draw on the eCRF. If the date or time of the last dose is unclear, provide the subject's best approximation. If the date or time of the last dose cannot be approximated, or if a PK sample cannot be collected within 48 hours of the liver chemistry event, do not obtain a PK sample. Instructions for sample handling and shipping are found in the Study Procedures Manual (SPM).
- Serum creatinine phosphokinase (CPK) and lactate dehydrogenase (LDH)

- Fractionate bilirubin, if total bilirubin ≥ 2 X upper limit of normal (ULN)
- Obtain a complete blood count (CBC) with differential to assess eosinophilia
- Record the appearance or worsening of clinical symptoms indicative of hepatitis or hypersensitivity, such as fatigue, nausea, vomiting, right upper quadrant pain or tenderness, fever, rash or eosinophilia as relevant on the AE eCRF
- Record the use of concomitant medications, including acetaminophen, herbal remedies or any other over the counter (OTC) medications, or any putative hepatotoxins, on the concomitant medication eCRF
- Record alcohol use on the liver event alcohol intake eCRF

The following assessments are required for subjects with ALT ≥ 3 X ULN and bilirubin ≥ 2 X ULN (>35% direct) but are optional for other abnormal liver chemistries:

- Anti-nuclear antibody, anti-smooth muscle antibody, and Type 1 anti-liver kidney microsomal antibodies
- Liver imaging (ultrasound, magnetic resonance imaging [MRI] or computed tomography [CT]) to evaluate liver disease

